9.2.2 Records Retention

Records of data generated in the course of the study shall be retained for at least 6 years and could be used for future research studies submitted and approved by the IRB.

10 SAFETY MONITORING

10.1 Adverse Event Reporting

This is a minimal risk study and there is no intervention apart from obtaining blood samples. The adverse event reporting and the reporting of unanticipated problems related to research will be limited to events directly related to the study procedures (venipuncture and breach of privacy/loss of confidentiality). All study-related unanticipated problems or adverse events will be recorded and reported.

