2 ABBREVIATIONS USED IN THE PROTOCOL

3 ABSTRACT

We propose an Interventional Study of the effects of Geisinger's Fresh Food Farmacy program on patient health. In particular, we will conduct a pragmatic, prospective, randomized-controlled trial of Geisinger's Fresh Food Farmacy (FFF) program.¹

In July 2016, Geisinger began piloting the "Fresh Food Farmacy" (FFF) program for diabetic, food insecure patients in northeastern Pennsylvania. Fresh Food Farmacy brings a "food-asmedicine" approach to communities to combat high rates of obesity, pre-diabetes, and diabetes. The program evolves over time, but the key elements include the following. Participants receive a referral to the Fresh Food Farmacy dietitian who provides a diet prescription for fresh food for themselves and their household, enough for 5 days a week, 2 meals a day. Participants also receive medication management services from a pharmacist, and receive case management services from a health manager or other health care professional. Their biometric measures (HbA1c, fasting glucose, weight, BMI, blood pressure, total cholesterol, LDL cholesterol, and triglycerides) and medication usage are tracked on a regular basis. In addition, participants receive a comprehensive suite of services, including diabetes wellness classes; dietary

consultations; workshops to discuss challenges to healthy eating and diabetes management; selfmanagement training (including monthly group classes); cooking expos; and a welcome kit with measuring cups/spoons, recipes, and nutritional and program information.

FFF has received considerable attention, as it uses a holistic approach to address a key "social determinant of health" and providers, public health officials, and payers are increasingly willing to consider innovative approaches to improve the health of patients. While the potential to benefit patients is high, there is a need for randomized-controlled trial evidence for such programs to establish their effectiveness.

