8 STUDY DESIGN- PROSPECTIVE STUDY

8.1 Description

This is a pragmatic, randomized, prospective research study. Qualifying subjects will be randomized 1:1 to receive either early participation in the FFF program (treatment group) or later participation (control group).

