12.3 Data Monitoring Plan

PI, [name], will oversee overall data safety and monitoring for the project. The Geisinger and MIT teams will continually assess the potential risks and participant safety throughout the study period and report to the PI. Further, the GIRB will review progress of the study per GIRB policy. Any protocol changes will be submitted to the IRB via a modification request and no changes will be implemented without IRB approval.

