### Planned Heterogeneity Analysis

In addition to outcome comparisons across all of the participants, we will consider heterogeneous treatment effects across patients. First, a priori we are interested in whether the program is especially effective for different levels of baseline HbA1c in order to help target the program in the future. For example, if effect sizes decrease with the baseline A1c, we may want to expand the program to those with A1c  $\geq$  7.5.

We are also interested in whether the program has different effects across the two locations (Scranton and Lewistown) to investigate the external validity of the estimates.

We will also test for different effects of the program by sex, as the cooking instruction may differ in effectiveness for men versus women. Household structure may be important given that the food goes to the household: differences between single and multi-person households will be estimated.

We hypothesize that the FFF program may have greater impacts among those of lower income (for whom the food may be especially helpful) and may vary across education levels (those with more education may be better able to utilize the information they are given about food preparation and diabetes management or they may already possess that information); these hypotheses will be tested using ZIP code level education and income measures, although there

may be little variation. We will also test differences by type of payer, with Medicaid providing another proxy for income as well as independent interest in effects for this group given interest among Medicaid systems in this type of intervention.

To further investigate the importance of information, we can compare results for individuals who score relatively well on the baseline survey questions about understanding of diabetes and diet. We will create a score for those questions and split the sample based on the median value of the initial knowledge. Another source of heterogeneity that could be considered in other contexts is the cost of using the program. We plan to compare results by distance between home and the clinic based on the median distance to the clinic from the residential ZIP code.

HbA1c can be affected by diet, lifestyle, and drug adherence. To consider the latter, we will compare patients who are on insulin versus those who are not on insulin at the start of the trial.

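### Adverse-event reporting leaves out the randomised programme: events related to it are not reported, hypoglycaemia is not a defined outcome, and only non-specific all-cause measures are compared by arm

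*Protocol*

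**What the plan says.** Protocol 10.1 reads: "This is a minimal risk study and there is no intervention apart from obtaining blood samples". Adverse-event reporting is then "limited to events directly related to the study procedures (venipuncture and breach of privacy/loss of confidentiality").

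The design sections describe something else. The protocol abstract opens: "We propose an Interventional Study of the effects of Geisinger's Fresh Food Farmacy program on patient health". Section 8.1 has subjects "randomized 1:1 to receive either early participation in the FFF program (treatment group) or later participation (control group"). The consent section (12.1) names the offer of food as the treatment and gives data confidentiality as the main risk. The abstract also lists a drug-related component: "Participants also receive medication management services from a pharmacist".

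On oversight, section 12.3 says: "The Geisinger and MIT teams will continually assess the potential risks and participant safety throughout the study period and report to the PI". It names no events, no data source and no comparison by arm.

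The SAP has no safety section. Its section 3.3 compares the arms on any inpatient stay, any ED visit, any hospital visit, visit counts, outpatient visits, medication use including insulin, and biomarkers including fasting glucose. Under Planned Heterogeneity Analysis it adds: "we will compare patients who are on insulin versus those who are not on insulin at the start of the trial". In both documents hypoglycaemia appears only in the title of a cited reference.

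**The concern.** The start of FFF is the randomised contrast. A safety section that recognises only blood draws as intervention puts any event caused by the programme outside adverse-event reporting by definition.

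Low glucose is a plausible example. The programme changes diet in patients with HbA1c of at least 8.0%, insulin use is not among the exclusions in protocol 8.2.3, and lower HbA1c is the aim. The documents give no rate for such events and do not settle their direction. That is a reason to tabulate them by arm.

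The protocol says the results will inform whether FFF is expanded at Geisinger or tried in other health systems. Run as written, the trial could report an HbA1c effect with no defined information on programme-related harm beside it. The HbA1c analysis itself is not affected.

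**Working it through.** **1. The passages side by side**

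| Place | What counts as the intervention |
|---|---|
| Protocol 10.1 | Blood sampling only |
| Protocol 3 | The FFF programme, in a study called interventional |
| Protocol 8.1 | Early versus later FFF, allocated 1:1 |
| Protocol 12.1 | The offer of food, named as the treatment |

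The first row cannot be squared with the other three as written.

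**2. How much could the planned all-cause comparison reveal?**

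Inputs from SAP Table 2, hospital visit 0-180 days: mean 0.39, SD 0.49, √(1−R²) 0.85, target MDE 30%, required N 397. The SAP states 80% power, alpha 0.05 and N = 500 for its HbA1c simulation. I use those values, two-sided, with 250 per arm and complete data.

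Reproducing the plan's figure:
- Adjusted SD = 0.49 × 0.85 = 0.4165; difference = 0.30 × 0.39 = 0.117.
- n per arm = 2 × (1.960 + 0.842)² × 0.4165² / 0.117² ≈ 199, so N = 398 against 397 stated. This reproduces. One-sided testing gives 314 and 90% power gives 534; neither fits.

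At 250 per arm:
- SE = 0.4165 × √(2/250) = 0.0373.
- Detectable difference at 80% power = 2.802 × 0.0373 ≈ 0.104, or 10.4 percentage points.
- Power ≈ Φ(excess/SE − 1.96). A 2-point excess gives Φ(0.54 − 1.96) ≈ 8%. A 5-point excess gives Φ(1.34 − 1.96) ≈ 27%.

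These are net excesses. A fall in other hospital visits, which the trial hopes for, would offset them.

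**3. How much would a dedicated tabulation reveal?**

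The documents give no hypoglycaemia rate. I assume 6-month control rates of 1% to 5% and a doubling, with 250 per arm and two-sided 0.05. Power = Φ((d − 1.96 × SE₀)/SE₁), where d is the difference, SE₀ uses the pooled rate and SE₁ the separate rates.

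| Assumed rates | SE₀ | SE₁ | Power |
|---|---|---|---|
| 1% v 2% | 0.0109 | 0.0109 | 15% |
| 2% v 4% | 0.0153 | 0.0152 | 26% |
| 3% v 6% | 0.0185 | 0.0185 | 37% |
| 5% v 10% | 0.0236 | 0.0235 | 57% |

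The gain is mainly in specificity: the events are named, counted and shown with an interval.

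**4. Are the data and the timing suitable?**

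Protocol 9.2.1 already requests admissions, medications, problem-list entries and lab values. At 6 months controls have not started FFF, so the contrast is clean. At 12 months it is 12 against 6 months of exposure.

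Low glucose lab values are different. Protocol 8.4 and 11.1 give treated subjects a research draw at month 0 that controls do not have. Only the draws at about months 6 and 12 are common to both arms.

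**The case against.** The strongest reply is that 10.1 concerns research procedures only. Protocol 12.1 says FFF is being rolled out whether or not a study takes place, and patients who decline the study still receive a randomised start date. On that view the research adds only labs, surveys and data use, and 10.1 is merely loosely worded. This explains the narrow scope. It does not remove the contradiction, because programme start is what the trial randomises and evaluates.

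Three other parts of the reply stand:

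- A reader might infer that harms are never compared between arms. The documents do not support that. SAP 3.3 compares ED, inpatient and outpatient use and medication use by arm, and a net increase in hospital care would show as an increase even though the outcome is framed as a benefit.
- A reader might infer that only needle and privacy events are recorded at all. That confuses adverse-event reporting with data capture: protocol 9.2.1 extracts all encounters, and 12.3 adds general oversight.
- A reader might infer that hypoglycaemia is the leading harm. The documents rank no harms. Pharmacist medication management appears in the protocol, but the SAP's description of the programme mentions only tracking of medication use.

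It is also fair that neither document plans a formal safety claim, so there is no stated safety conclusion to call wrong.

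**Conclusion.** The point holds in a limited form. Section 10.1 contradicts protocol sections 3, 8.1 and 12.1 on what the intervention is. Programme-related events consequently fall outside adverse-event reporting, and hypoglycaemia is not a defined outcome in either document. The by-arm comparisons that do exist are non-specific and weak for this purpose: about 8% power for a 2-point net excess in hospital visits and about 27% for 5 points. Those figures rest on Table 2's SD and adjustment factor, 250 per arm and no attrition.

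A named tabulation would also be underpowered, at about 15% to 57% for a doubling. That range rests entirely on assumed rates of 1% to 5%. The case for it is that it identifies the events at little cost, not that it would settle the question. The change should be made, but neither the primary analysis nor the sample size depends on it.

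**What to change.** 1. Reconcile the sentence in protocol 10.1 with sections 3, 8.1 and 12.1, and state how programme-related events are treated.
2. Add to SAP 3.3 a descriptive safety tabulation by randomised arm, at 6 months (before controls start) and 12 months, of ED or inpatient encounters with a hypoglycaemia diagnosis. Give counts, the difference and a confidence interval, overall and by baseline insulin use.
3. Show outpatient-coded events separately and label them as open to unequal detection, since the treated arm is seen more often.
4. Do not compare ad hoc low glucose lab values between arms. If lab values are shown, use only the month-6 and month-12 draws common to both arms.
5. Name who receives the by-arm tabulation. Section 12.3 sends safety reports to the PI, while protocol 9.1.1 and SAP section 4 keep the clinician team blind to interim results; the arrangement must be consistent with both.

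Cost: a short protocol amendment, one added SAP item, a diagnosis code list and some programming on data already requested. No new visits and no change in sample size are needed. The remaining downside is that the comparison is descriptive and imprecise, and should be labelled so.

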11 SAMPLE COLLECTION AND RETENTION

11.1 Collection

As outlined in Section 8.4 of this protocol, subjects in the treatment group will provide a blood sample for research purposes prior to beginning the FFF program, at 6 months and 12 months. Subjects in the control group will provide a blood sample for research purposes prior to the beginning the FFF program (6 months into the study) and again after 6 months in the program (12 months in the study). Processing will be completed in a Geisinger Laboratory and testing completed according to institutional policy.

[figure not shown]
11.1.1 Total Volume of Blood Collected

The total volume of blood collected from each subject will be approximately 30 mL.

11.2 Retention

Records of data generated in the course of the study shall be retained for at least 6 years and could be used for future research studies submitted and approved by the IRB.

Identifiable samples can be destroyed at any time at the request of the subject.

12 PROTECTION OF HUMAN SUBJECTS

12.1 Informed Consent and HIPAA Authorization

[figure not shown]
We are requesting a waiver from written informed consent and HIPAA authorization for subjects consented to FFF study. Instead, we will request verbal consent from study participants. The study will be described during the initial outreach prior to the patient's initial visit. A follow-up information sheet will be sent via mail reiterating the FFF study details, the fact that a study is occurring, and that the participant may choose to end study participation at any time.

We are requesting this verbal consent with follow-up information instead of an in person written consent for three reasons. First, this is a pragmatic trial in that the program is being rolled out to new participants in a randomized way to smooth the onboarding process. This process is largely done by phone and our study staff will not be in the areas where the subjects are being recruited. Second, written consent in this context could undermine the program. For written consent we would need subjects to go to the FFF clinic, as home visits would not be feasible. Such a visit would expose both the treatment and control group to the information campaigns hosted there and may dampen the enthusiasm for the program for anyone not beginning the program until a later date.

Third, the study represents minimal risk to patients because the treatment is the offer of healthy, fresh food, and the main risks are data confidentiality. These risks will be dealt with by sending only a limited data set to researchers at MIT under a data use agreement complete with review by Geisinger's Information Security/Privacy Office. Furthermore, the program is being rolled out regardless of whether a study occurs or not. Last, the patient will not incur a cost to enroll in the program or have their outcomes measured.

For those who decline consent to be in the study, they will still enter the program based on their control or treatment status as determined by the pre-randomization, as this is the way the program is being rolled out in an equitable fashion: if we were to allow those who

CONFIDENTIAL AND PROPRIETARY

do not consent to enter the program sooner, this would delay the entry of others. In addition, allowing earlier entry to those who do not participate could lead to sample attrition from the control group, rendering the trial infeasible. Data for those who refuse consent will not be analyzed as part of the study, except for the

eligibility variables that will be compared to those who did consent so that the study population can be placed in context.

We also stress that given the lack of randomized controlled trial evidence for this type of program, there is scientific equipoise as to whether this program is effective.

[figure not shown]
Household members of study participants

Household members may benefit from the program and we would like to measure effects for this group using administrative data. Study subjects will be informed of this as part of the consent process.

Household members are secondary subjects, however, and we are requesting a waiver of consent and HIPAA authorization. Household members are identified by the subject to ensure an accurate listing of household members who are actively benefiting from the program. Pulling data using the same address may lead to including household members who are not actively living in the residence (e.g. college student who is not living at home). Our request for the waivers are due to:

1. The study represents minimal risk to the household members because we will only analyze secondary data and will not contact them. The main risks are data confidentiality. These risks will be dealt with by sending only a limited data set to researchers at MIT under a data use agreement complete with review by Geisinger's Information Security/Privacy Office.

2. It is not practical to carry out the research if each of these secondary research subjects needed to be contacted.

Retrospective data analysis

The retrospective data analysis will use previously existing data to compare program participants to similar patients. We are requesting a waiver of consent and HIPAA authorization for this analysis because consenting 20,000 patients is infeasible given the retrospective nature of the research. We propose that this portion of the research carries minimal risks to patients, as the primary risk is data breach, the risk of which is minimized as described above and below.

12.2 Protection of Human Subjects Against Risks

[figure not shown]
The program provides nutrition advice and fresh food to recipients. The main risk to subjects is data confidentiality. As a result, we take a number of steps to protect subjects' private data.

Identifiable data will remain on Geisinger's internal servers. A deidentified study ID will be assigned to each participant and the table matching patient identifiers with the study IDs will be stored on a password-protected, encrypted file on Geisinger's internal server. Only key data study personnel will have access to this linked file.

A limited data set will be constructed that will be stripped of name, address, medical record number, and social security number. Dates of service and zip code of residence will be present. It will include the unique, scrambled identifiers for subject ID.

The limited dataset set will be transferred securely to MIT under a Data Use Agreement with Geisinger, complete with review by the Information Security/Privacy Office.

Data at MIT will be stored on an institutional stationary server restricted to authorized hosts and users using IP-based host lists and Kerberos credentials. Kerberos credentials are assigned to specific individuals who are associated with MIT. All computations and analytical work will be performed exclusively on these servers. File based permissions will be set to restrict data access

to the research team. Remote access to this server will be provided using the encrypted SSH protocol and require strong passwords. The data security at MIT is managed by a dedicated staff of IT professionals. This support includes account management, security patching, software installation and host monitoring. Data is backed-up to a secondary NAS device which is accessible only by IT personnel.

No attempts by members of the MIT team will be made to identify or contact individual patients. Any publications of analysis or data will include only aggregated data not linked to any individual.

12.3 Data Monitoring Plan

PI, [name], will oversee overall data safety and monitoring for the project. The Geisinger and MIT teams will continually assess the potential risks and participant safety throughout the study period and report to the PI. Further, the GIRB will review progress of the study per GIRB policy. Any protocol changes will be submitted to the IRB via a modification request and no changes will be implemented without IRB approval.

13 PUBLICATION PLAN

We plan to apply for grant funding to supplement the enrollment and oversight at Geisinger and publish a manuscript in a peer-reviewed journal.

One year after the initial publication, we will seek to publish fully-deidentified data as is common for NIH-funded studies.³⁰ The contents of such data will be governed by a Data Use Agreement between MIT and Geisinger.

#### Abstract

We will conduct a randomized controlled trial to estimate the impact of Geisinger Health's Fresh Food Farmacy program (FFF). The program brings a "food-as-medicine" approach to address a key social determinant of health (food insecurity) for patients with diabetes. A Fresh Food Farmacy dietitian prescribes enough fresh food for two meals per day, five days per week, for everyone in the patient's household. Prescriptions for the food are filled once a week at no charge at a local clinic. Complementary services include dietitian consultation, recipes, cooking classes, biometric tracking, diabetes self-management training and checks that participants are following best practices such as eye and foot exams. By randomly assigning patients to either start the FFF program immediately or in six months, we will be able to estimate the impact of the FFF program on a wide range of clinical outcomes, healthy behaviors, measures of wellbeing, and health care utilization.

PRINCIPAL INVESTIGATORS: [name], DO MBA and [name], PhD

CO-INVESTIGATOR(S): [name], MD, PhD, [name], PhD, [name], [name], RN

